11. STUDY MONITORING AND COMPLIANCE

All aspects of the study will be carefully monitored by the sponsor or authorized representatives of the sponsor, with respect to current good clinical practices and standard operating procedures for compliance with applicable government regulations. These individuals will have access, both during the trial and after trial completion, to review and audit all records necessary to ensure integrity of the data, and will periodically review progress of the study with the principal investigator.

Every attempt must be made to follow the protocol and to obtain and record all data requested for each subject at the specified times. However, ethical reasons may warrant the failure to obtain and record certain data, or to record data at the times specified. If this becomes necessary, the reasons for such must be clearly documented on the case report form.

12. PROTOCOL DEVIATION REPORTING

Emergent deviations or amendments may be initiated without prior Sponsor or IRB/ERC approval, only in cases where the change(s) is /are necessary to eliminate an immediate apparent hazard. A protocol deviation is defined as an isolated occurrence involving a procedure that did not follow the study protocol, or study specific procedures.

The timeline for reporting protocol deviations to the Office of Research Management (ORM) WRAIR HURC and, if an IND study, Regulatory Compliance and Quality/USAMRMC HSRRB is determined by the categorization of the deviation: (1) emergent/significant or (2) non emergent/minor. Unanticipated problems should be reported in the appropriate timeframe according to the seriousness of the event as an SAE, a significant deviation, or a minor deviation.

Emergent/Significant deviations are departures from protocol that have a significant impact on the welfare or safety of a volunteer or on the integrity of the study data. Examples: administering the wrong test article to a volunteer; failure to obtain a scheduled blood draw for multiple participants. Significant deviations that occur in minimal risk and greater than minimal risk protocol will be reported to the sponsor (as required) and through the Office of Research Management (ORM) and WRAIR Human Use Review Committee, and if a greater than minimal risk (GTMR) protocol, to the Office of Research Protections, USAMRMC, immediately by phone and in writing within 5 business days of becoming aware of the deviation. Non Emergent/Minor deviations are routine departures that typically involve a volunteer's failure to comply with the protocol. Examples: missing scheduled visits; failing to return diary cards.

Minor deviations that occur in minimal risk and greater than minimal risk protocols will be reported to the sponsor (as required) and the Office of Research Management/HURC in a summary report with the annual continuing review report. A cumulative deviation report will be submitted to the ORM with each protocol continuing review report or with the final report, whichever comes first.

13. RETENTION OF RECORDS

Because data from clinical trials sponsored by the Office of the Surgeon General, Department of the Army (OTSG) may be used to support regulatory filings in several countries throughout the world, the policy concerning record retention reflects the most stringent current guidelines (those of the Committee for Proprietary Medicinal Products, or CPMP, in Europe). To comply with the CPMP guidelines, WRAIR requests that the investigator arrange for the retention of case report forms, source records, and other supporting documentation for a minimum of 15 years.

14. USE OF INFORMATION AND PUBLICATION

The investigator understands that the information generated in this study will be used by the sponsor in connection with the development of the product and therefore may be disclosed to government agencies in various countries. To allow for the use of information derived from the study, it is understood that the investigator is obliged to provide the sponsor with complete test results, all study data, and access to all study records.

WRAIR recognizes the importance of communicating medical study data and therefore encourages their publication in reputable scientific journals and at seminars or conferences.

Any results of medical investigations with Aventis Pasteur products and/or publication/lecture/manuscripts based thereon, shall be exchanged and discussed by the investigator, the manufacturer's representative(s), and the U.S. Army Medical Research and Materiel Command 30 days prior to submission for publication or presentation.

Results from investigations shall not be made available to any third party by the investigating team outside the publication procedure as outlined previously. WRAIR will not quote from publications by investigators in its scientific information and/or promotional material without full acknowledgment of the source (i.e., author and reference).

15. PROTOCOL AMENDMENTS

Only the sponsor may modify the protocol. Amendments to the protocol will be made only after consultation and agreement between sponsor and investigator. The only exception is where the investigator considers that a subject's safety is compromised without immediate action. In these circumstances, immediate approval of the chairman of the HSRRB and IRB must be sought, and the investigator should inform the sponsor and the full boards within 5 working days after the emergency occurred. All amendments that have an impact on subject risk or the study objectives, or require revision of the informed consent document, must receive approval from the HSRRB and all IRBs prior to their implementation. Minimal risk ammendments must be reviewed and approved prior to implementation.

16. **REFERENCES**

1. UNAIDS/WHO. AIDS epidemicupdate: December 1999.

2. Quinn TC. Global burden of the HIV pandemic. Lancet 348:99-106 (1996).

3. Steinman, R.M. & Witmer, M.D. Lymphoid dendritic cells are potent stimulators of the primary mixed leukocyte reaction in mice. *Proc. Natl. Acad. Sci.* USA 75, 5132-5136 (1978).

5. Inaba, K. & Steinman, R.M. Protein-specific helper T lymphocyte formation initiated by dendritic cells. *Science* 229, 475-479 (1985).

18. APPENDICES

18.1 Statement of Obligations of Sponsor/Monitor and Clinical Investigator

Sponsor/Monitor

The sponsor or his/her designated representative, the monitor, will:

- 1. Conduct a pre-investigation visit to:
 - a. Establish the acceptability of the facility and record this in a written report (memorandum or form).
 - b. Discuss the proposed clinical trial with the investigator, supply the case report form, the Investigator Brochure, and the draft protocol for review and approval.
 - c. Discuss with the investigator FDA requirements with respect to informed consent, Institutional Review Board (IRB) approval of the trial, the protocol, including protocol amendments and informed consent changes.
- 2. Conduct periodic on-site visits to:
 - a. Assure adherence to the protocol.
 - b. Review case report forms and medical records for accuracy and completeness of information.
 - c. Examine pharmacy records for documentation of: quantity and date of receipt of investigational vaccine, dispensation and accountability data for vaccine administration to each subject, loss of materials, contamination, etc, and unused supplies.
 - d. Record, report (summarize) observations on the progress of the trial and continued acceptability of the facilities; prepare an on-site visit report.
 - e. Review investigator files for required documents, i.e., protocols, protocol amendments, IRB approvals (protocols, amendments, informed consent, etc), IRB charter and membership, communications to and from the IRB and the monitor.

Clinical Investigator

1. Institutional Review Board (IRB)

The investigator must assure the monitor that the IRB: a. Meets FDA regulations as defined in 21 CFR Part 56.

b. Has authority delegated by the parent institution and found in IRB by-laws, operation guidelines or charter to approve, or disapprove, clinical trials and protocols including informed consent and other documents (protocol amendments, information to be supplied to subjects concerning informed consent, etc).

- c. Complies with proper personnel makeup of IRB.
- d. Convenes meetings using acceptable rules of order for making decisions, recording such decisions and implementing them.
- e. Files contain (a) documentation of its decisions such as are found in IRB minutes and correspondence, (b) written guidelines or by-laws governing IRB functions, (c) protocols, (d) protocol information to be supplied to the subject, (f) correspondence between IRB and investigator (consent changes, protocol amendments, etc).
- 2. Informed Consent of Human Subjects.

The investigator must assure monitor that the informed consent for a subject:

- a. Meets FDA regulations as defined in 21 CFR Part 50 Informed Consent.
- b. Has been approved by the IRB, including, when required, information to be given to the subject regarding the trial he/she is enrolled in.

(1) Informed consent includes the basic elements and any additional elements necessary.

(2) The subject and a study site representative sign the form and the subject is given a copy.

3. Storage and Dispensing of Vaccine Supplies.

The investigator (or pharmacist) must assure (demonstrate to) the monitor that:

- a. Adequate and accurate written records show receipt and disposition of all vaccine supplies, including dates, serial or lot number, quantities received, each quantity dispensed, administered or used with identification of each subject.
- b. Purpose and reasons are given in written records for vaccine disposal, i.e., the amount contaminated, broken, or lost, etc, and quantity returned to the sponsor.
- 4. Case Report Forms.

The investigator must assure the monitor that:

- a. Case report forms, when completed, accurately reflect the medical records on each subject or patient.
- b. Case report forms and medical records will be accessible to the monitor or FDA inspectors' on-site visits.
- 5. Files and Records.

The investigator must assure the quality, integrity, and content of his/her files that will be inspected by the monitor and FDA inspectors. The files must contain, as a minimum: a. Correspondence to and from IRB and the monitor.

- b. Documents that include:
 - (1) IRB-approved protocols.
 - (2) IRB-approved protocol amendments.
 - (3) IRB-approved informed consent and information supplied to the subject or subject.
 - (4) IRB charter, membership, and their qualifications.

- c. Documents and records must be retained for a minimum of 15 years.
- b. Clinical supplies:
 - (1) Record of receipt, date and quantity, batch or lot number.
 - (2) Disposition dates and quantity administered to each subject.
- 6. Inventory records.

Statement of Obligations and Responsibilities of the Medical monitor:

The medical monitor is required to review all serious and unexpected adverse events (per ICH definitions) associated with the protocol and provide an unbiased written report of the event within 10 calendar days of the initial report. At a minimum, the medical monitor should comment on the outcomes of the adverse event (AE) and relationship of the AE to the test article. The medical monitor should also indicate whether he/she concurs with the details of the report provided by the study investigator.

One incorrect response is acceptable. The volunteer can get education about the misunderstanding and sign the Informed Consent form. If more than one response is incorrect, the participants will receive education and will take the TOU again at the same visit or at the next visit (for a maximum of 3 attempts to pass the test).

18.4 PREGNANCY REPORTING

For subjects who become pregnant after completing the third immunization: The subject may continue on the study with all scheduled visits, but no further immunizations will be given. For all subjects who become pregnant while on the trial (including those mentioned above), a Pregnancy Report CRF should be completed as soon as possible. The site should maintain contact with pregnant subjects to obtain pregnancy outcome information for the Pregnancy Follow-up CRF.

Specific information to be collected includes the following:

- 1. Pregnancy Report
 - Date of last menstrual period, date pregnancy confirmed, estimated date of confinement, history of children born with congenital abnormalities, and history of spontaneous abortions.
- 2. Pregnancy Follow-up
 - Date of delivery or termination, outcome of pregnancy (i.e., spontaneous abortion, therapeutic abortion, ectopic pregnancy, stillborn delivery, liveborn delivery) and the presence or absence of congenital abnormalities in the infant.
- 3. Abnormal Pregnancy Outcome-mother (To be completed in the event of a delivery of an infant with congenital abnormalities.)
 - Complications during pregnancy, labor and delivery; information regarding prenatal care, infections, illnesses, and medications taken during pregnancy; use of drugs, alcohol, or other conditions during the course of the pregnancy.
- 4. Abnormal Pregnancy Outcome-infant (To be completed in the event of a delivery of an infant with congenital abnormalities.)
 - The sex, weight, estimated gestational age, and description of abnormalities present in the infant.

18.6 Toxicity Grading Scale

TABLE FOR GRADING SEVERITY OF ADULT ADVERSE EXPERIENCES

PARAMETER	GRADE 1 MILD	GRADE 2 MODERATE	GRADE 3 SEVERE	GRADE 4 POTENTIALLY LIFE THREATENING
HEMATOLOGY				
Hemoglobin	9.5 g/dL - 10.5 g/dL	8.0 g/dL - 9.4 g/dL	7.9 g/dL - 6.5 g/dL	<6.5 g/dL
Absolute Neutrophil Count	1000 - 1500/mm3	750 - 999/mm3	500 - 749/mm3	<500/mm3
WBC	>13,000	>15,000	>20,000	>30,000 or <1,000
Percent Polys + Bands	>80%	90%	≥95%	
Platelets	100,000 - 120,000/mm3	75,000 - 99,999/mm3	50,000 - 74,999/mm3	20,000 - <50,000/mm3
CD4 Counts Uninfected	300 - 400/mm3 <300 or <20%	300/mm3 <200 or <18%	200/mm3 <100 or 15%	<100/mm3 <50 or <12%
Fibrinogen	100 - 200 mg/dL OR 400 - 600 mg/dL	<100 mg/dL OR >600 mg/dL	<50 mg/dL or associated with gross bleeding OR associated with disseminated coagulation	
Prothrombin Time (PT)	>1.0 - 1.24 x ULN	>1.25 - 1.49 x ULN	>1.5 - 3.0 x ULN	>3.0 x ULN
PTT	>1.0 - 1.66 x ULN	>1.66 - 2.33 x ULN	>2.33 - 3.0 x ULN	>3.0 x ULN
CHEMISTRIES				
СРК	≥4 ULN	≥6 ULN	≥10 ULN	≥20 ULN
Creatinine	>1.0 - 1.5 x ULN	>1.5 - 1.9 x ULN	>2.0 - 6.0 x ULN	>6.0 x ULN

SODIUM Hyponatremia Hypernatremia	130 - 135 meq/L 146 - 150 meq/L	123 - 129 meq/L 151 - 157 meq/L	116 - 122 meq/L 158 - 165 meq/L	<116 meq/L >165 meq/L
POTASSIUM Hyperkalemia Hypokalemia	5.0 5.5 meq/L 3.2 - 3.4 meq/L	5.6 - 6.0 meq/L 3.0 - 3.1 meq/L	6.1 - 6.5 meq/L 2.5 - 2.9 meq/L	>6.6 meq/L <2.5 meq/L
PHOSPHATE Hypophosphatemia	2.0 - 2.4 mg/dL	1.5 - 1.9 mg/dL	1.0 - 1.4 mg/dL	<1.0 mg/dL
CALCIUM (corrected for albumin) Hypocalcemia Hypercalcemia MAGNESIUM	7.8 - 8.4 mg/dL 10.6 - 11.5 mg/dL	7.0 - 7.7 mg/dL 11.6 - 12.5 mg/dL	6.1 - 6.9 mg/dL 12.6 - 13.5 mg/dL	<6.1 mg/dL >13.5 mg/dL
Hypomagnesemia	1.2 - 1.4 meq/L	0.9 - 1.1 meq/L	0.6 - 0.8 meq/L	<0.6 meq/L
BILIRUBIN Hyperbilirubinema	>1.0 - 1.5 x ULN	>1.5 - 2.5 x ULN	>2.5 - 5 x ULN	>5 x ULN
GLUCOSE Hypoglycemia Hyperglycemia (nonfasting and no prior diabetes)	55 - 64 mg/dL 116 - 160 mg/dL	40 - 54 mg/dL 161 - 250 mg/dL	30 - 39 mg/dL 251 - 500 mg/dL	<30 mg/dL >500 mg/dL
Triglycerides		400 - 750 mg/dL	751 - 1200 mg/dL	>1200 mg/dL
URIC ACID Hyperuricemia	7.5 - 10.0 mg/dL	10.1 - 12.0 mg/dL	12.1 - 15.0 mg/dL	>15.0 mg/dL
LIVER TRANSAMINASE AST (SGOT) ALT (SGPT) GGT Alk Phos	1.51 - 2.5 x ULN 1.51 - 3.0 x ULN 1.51 - 2.5 x ULN 1.51 - 2.5 x ULN	>2.5 - 5.0 x ULN >3.0 - 5.0 x ULN >2.5 - 5.0 x ULN >2.5 - 5.0 x ULN	>5.0 - 10.0 x ULN >5.0 - 10.0 x ULN >5.0 - 10.0 x ULN >5.0 - 10.0 x ULN	>10.0 x ULN >10.0 x ULN >10.0 x ULN >10.0 x ULN

KV 138			22 Au	Version 2.15 22 August 2006		
PANCREATIC ENZYMES Amylase Pancreatic amylase Lipase	>1.0 - 1.5 x ULN >1.0 - 1.5 x ULN >1.0 - 1.5 x ULN	>1.5 - 2.0 x ULN >1.5 - 2.0 x ULN >1.5 - 2.0 x ULN	>2.0 - 5.0 x ULN >2.0 - 5.0 x ULN >2.0 - 5.0 x ULN	>5.0 x ULN >5.0 x ULN >5.0 x ULN		
CARDIO- VASCULAR						
Cardiac Arrhythmia		Asymptomatic; transient dysrhythmia, no Rx req	Recurrent/persiste nt dysrhythmia; symptomatic Rx req	Unstable dysrhythmia, hospitalization and Rx req		
Hypertension	Transient, increase >20 mm Hg diastolic BP; no Rx req	Recurrent; chronic increase >20 mm Hg diastolic BP; Rx req	Acute Rx req; outpatient OR hospitalization possible	Hospitalization req OR end organ damage		
Hypotension	Transient orthostatic hypotension with heart rate increased by >20 beats/min OR decreased by <10 mm Hg systolic BP, no Rx req	Symptoms OR BP decreased by <20 mm Hg systolic, correctable with oral fluid Rx	IV fluid req OR hospitalization	Mean arterial pressure <60 mm HG OR end organ damage OR shock, vasopressor Rx req		
Pericarditis	Minimal effusion	Mild/mod asymptomatic effusion, no Rx	Symptomatic effusion, pain, EKG changes	Tamponade OR pericardiocentesis OR surgery req		
Hemorrhage, blood loss		Mildly symptomatic, no Rx req	Gross blood loss OR 1-2 units transfused	Massive blood loss OR >2 unites transfused		
Nausea	Mild OR transient; reasonable intake maintained	Mod discomfort OR intake decreased for <3 days	Severe discomfort OR minimal intake for ≥3 days	Hospitalization req		

Version 2.15

Vomiting	Mild OR transient; 2-3 episodes per day OR mild vomiting lasting <1 week	Mod OR persistent; 4-5 episodes per day; OR vomiting lasting ≥1 week	Severe vomiting of all food/fluids in 24 hrs OR orthostatic hypotension OR IV Rx req	Hypotensive shock OR hospitalization req for IV Rx req
Diarrhea	Mild OR transient, 3-4 loose stools per day OR mild diarrhea lasting <1 week	Mod OR persistent; 5-10 loose stools per day OR diarrhea lasting \geq 1 week	>10 loose stools/day, bloody diarrhea; OR orthostatic hypotension OR electrolyte imbalance, >2 L IV fluid req	Hypotensive shock OR severe electrolyte imbalance
Oral Discomfort/Dysphagia	difficulty	Difficulty swallowing but able to eat and drink	Unable to swallow solids	Unable to drink fluids; IV fluids req
Constipation	swallowing	Moderate abdominal pain 78 hours with impaction require output prescription	Requiring disimpaction or hospital treatment	Distention with vomiting OR obstipation
RESPIRATORY				
Cough (for aerosol studies)	Transient; no Rx	Treatment associated cough; inhaled bronchodilator	Uncontrolled cough; systemic Rx req	
Bronchospasm Acute	Transient; no Rx; FEV1 or peak flow reduced to 70% - 80%	Rx req; normalizes with bronchodilator; FEV1 or peak flow 50%-69%	No normalization with bronchodilator; FEV1 or peak flow 25%-49%, retractions	Cyanosis; FEV1 or peak flow <25% OR intubated
Dyspnea	Dyspnea on exertion	Dyspnea with normal activity	Dyspnea at rest	Dyspnea requiring O ₂ therapy

NEUROLOGIC				
Neuro-cerebellar	Slight incoordination OR dysdiadochokin esia	Intention tremor OR dysmetria OR slurred speech OR nystagmus	Ataxis requiring assistance to walk or arm incoordination interfering with ADLs	Unable to stand
Neuro-psych/mood			Severe mood changes requiring medical intervention; suicidal ideation	Acute psychosis req hospitalization; suicidal gesture/attempts
Paresthesia (burning, tingling, etc.)	Mild discomfort; no Rx req	Mod discomfort; non-narcotic analgesia req	Severe discomfort; OR narcotic analgesia req with symptomatic improvement	Incapacitating; OR not responsive to narcotic analgesia
Neuro-motor	Mild weakness in muscle of feet but able to walk and/or mild increase or decrease in reflexes	Mod weakness in feet (unable to walk on heels and/or toes), mild weakness in hands, still able to do most hand tasks and/or loss of previously present reflex or development of hyperreflexia and/or unable to do deep knee bends due to weakness	Marked distal weakness (unable to dorsiflex toes or foot drop, and mod proximal weakness e.g. , in hands interfering with ADLs and/or req assistance to walk and/or unable to rise from chair unassisted	Confined to bed or wheel chair because of muscle weakness

NEUROLOGIC

Neuro-sensory	Mild impairment (decreased sensation, e.g. , vibratory, pinprick, hot/cold in great toes) in focal area or symmetrical distribution	Mod impairment (mod decreased sensation, e.g. , vibratory, pinprick, hot/cold to ankles) and/or joint position or mild impairment that is not symmetrical	Severe impairment (decreased or loss of sensation to knees or wrists) or loss of sensation of at least mod degree in multiple different body areas (i.e. , upper and lower extremities)	Sensory loss involves limbs and trunk
MUSCULO- SKELETAL				
Arthralgia/Arthritis	Arthralgia	Arthralgia with joint effusion or moderate impairment of activity	Frank arthritis with or without effusion OR resulting in severe impairment of activity	
Myalgia	Myalgia without limitation of activity	Muscle tenderness at other than injection site or with moderate impairment of activity	Frank myonecrosis OR with severe impairment of activity	
CUTANEOUS				
Rash/Dermatitis	Erythema, pruritus	Diffuse maculopapular rash OR dry desquamation	Vesiculation OR moist desquamation OR ulceration	ANY ONE: mucous membrane involvement, suspected Stevens- Johnson (TEN), erythema multiforme, necrosis req surgery, exfoliative dermatitis

Local Reaction	Erythema OR induration <15 x 15 cm (225 cm ²)	Erythema, induration, or edema >15 x 15 cm (225 cm ²)	Ulceration OR super infection OR phlebitis	Necrosis of the skin
URINALYSIS				
Proteinuria Random urine	1+	2-3+	4+	Nephrotic syndrome
24 Hour Urine	200 mg - 1 g loss/day OR <0.3% OR <3 g/L	1-2 g loss/day OR 0.3 - 1.0% OR 3-10 g/L	2-3.5 g loss/day OR >1.0% OR >10 g/L	Nephrotic syndrome OR >3.5 g loss/day
Hematuria	Microscopic only £10 rbc/hpf	>10 rbc/hpf	Gross, with or without clots OR RBC casts	Obstructive OR transfusion req
MISCELLANEOUS				
Fever oral >12 hours	37.7 - 38.9C (100.0 - 101.5F)	39.0 - 39.5C (101.6 - 102.9F) OR max temp of 103F	39.6 - 40.5C (103 - 105F) OR max temp of 103.5F	>40.5C (105F) OR max temp >105F
Headache	Mild, no Rx req, OR non- narcotic analgesia Rx	Mod; OR responds to initial narcotic Rx	Severe; intractable; OR req repeated narcotic Rx	Req hospitalization, associated with neurologic, respiratory or cardiovascular abnormalities
Allergic Reaction	Pruritus without rash at injection site	Localized urticaria at injection site	Generalized urticaria angioedema	Anaphylaxis
ADL	Normal activity reduced <48 hours	Normal activity reduced 25%- 50% >48 hours	Normal activity reduced >50%; cannot work >48 hours	Unable to care for self

RV 138		Version 2.15 22 August 2006	
EYE	Mild pain, visual changes, conjunctival erythema, abnormal slit lamp	Loss of vision, clinically diagnosed uveitis, moderate to severe pain, glaucoma	

ADL = Activities of Daily Living

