4. Obtain interim history and physical, including vital signs and abbreviated risk assessment.

5. Perform risk behavior avoidance counseling and provide HIV test counseling.

6. Collect samples for HIV serology (1 ml red top).

7. Collect samples for immunogenicity (40 ml anticoagulated blood): LPA, neutralizing antibody, CTL, and ELISPOT. Separately and additionally, draw 3 ml of blood into a heparinized pediatric tube (no substitutions) PRIOR to immunization (whole blood ICC).

8. Administer vaccine injection(s) into the deltoid muscle (IM), or intradermally on the volar aspect of the arm (ID). The autologous DC are prepared from the pre-study leukopheresis. The DC are counted, checked for sterility, identity and potency and after being cleared for release, injected into the superficial subcutaneous space on the ventral inner aspect of the arm in two 0.2 ml aliquots. See details in **Appendix A** for specifics on dendritic cell release criteria, counts and maturity. Examine the injection sites for local reactions at 60 minutes post-injection and instruct subject in the evaluation of these local reactions; observe and instruct while the subject takes temperature (as guided for subsequent evaluations); enter findings on appropriate CRF.

9. Subjects will record daily symptoms for 7 days post-immunization (including the day of immunization), and will be instructed to contact the investigator if any untoward effects occur.

24-48 hour contact after the first immunization:

Subjects will be contacted by staff within 24 to 48 hours post-immunization (by telephone, by home visit, or by the other prearranged mechanism) to determine whether adverse effects have occurred. Subjects will be queried using a predetermined review of systems/reactogenicity worksheet. If the adverse effects experienced by the volunteer are deemed "moderate", he/she will be asked to return to clinic for evaluation by the investigator. Additional contacts will be arranged as indicated.

Visit 3: Day 14 (+/-4 days) after initial vaccination: Safety Evaluation

1. Collect diary, obtain interim history and physical.

2. Collect sample for CBC.

3. Collect sample for Chem-7, LFT's (Na, K, Cl, HCO3, Cr, BUN, Glc, AST, ALT, Total Bili, alk phos).

4. Collect urine for dipstick. If urine protein or blood is 1+ or greater, obtain a complete UA.

Visit 4: Day 28 (+/- 7 days) after initial vaccination:

Second vaccination

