6.6.2.3 Other Adverse Events

An adverse event is any undesired, noxious or pathological change in a patient or subject as indicated by physical signs, symptoms, and/or laboratory changes that occurs following administration of one of the vaccines, whether or not considered vaccine related. This definition includes intercurrent illnesses or injuries, and exacerbation of pre-existing conditions. The following information will be included in IND adverse event reports: Subject identification number and initials; investigator's name and name of MTF; subject's date of birth, gender, and ethnicity; test article and dates of administration; signs/symptoms and severity; date of onset; date of resolution or death; relationship to the study drug; action taken; concomitant medication(s) including dose, route, and duration of treatment; date of last dose; and HSSRB protocol Log No A-9906.

Local reactions to immunization and selected systemic events will be solicited via subject interview and will be recorded on the post-injection reaction form. Reactions occurring within 7 days postimmunization will be recorded on a reactogenicity form. All other adverse events will be recorded on the adverse event form. All adverse events occurring up to 30 days after the fourth injections will be collected. After that, i.e., after visit 12 at week 37, only adverse events that are serious and/or necessitate a physician's visit or a prescribed medication will be collected. The subject should be followed carefully until the condition is resolved and/or the cause is identified. Any medication or other therapeutic measure taken to relieve symptoms of the medical problem must be recorded on the appropriate case report form page(s) in addition to the outcome of the adverse event.

Where a diagnosis is possible, it is preferable to report this rather than a series of terms relating to the diagnosis. When reporting a syndrome, indicate the associated signs and symptoms parenthetically following the syndrome rather than as separate events.

The *severity of events* reported on the adverse event form will be determined by the investigator, based on the Toxicity Grading Scale (Appendix 17.6) or if the event is not listed the event will be graded following these guidelines:

Mild (Grade 1):	Transient or mild discomfort. No limitation in normal daily activity.
Moderate (Grade 2):	Some limitation in normal daily activity.
Severe (Grade 3):	Unable to perform normal daily activity.

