6.9.2.1 Postimmunization Reactions (Local and Systemic)

The maximal severity of local and systemic postimmunization reactions occurring in the seven days following each immunization and any immunization will be tabulated by group. Local reactions tabulated will include: injection site pain, erythema, induration, and temperature. Systemic reactions reported within seven days postimmunization will include: chills, nausea, malaise, myalgia, arthralgia, headache, rash and fever (as described in Toxicity Grading Scale, p. 58). Additionally, pain on injection will be noted. Frequencies and percentages of subjects experiencing each reaction will be presented for each symptom severity. If a reaction occurs more than once for a subject, the reaction will be classified according to the highest occurring severity and closest vaccine relationship.

Summary tables showing the occurrence of any local or systemic reaction overall and at each time point will also be presented.

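### The Celsius and Fahrenheit fever bands in the Toxicity Grading Scale do not convert at the inner limits, and no governing unit is named: 101.6–102.1 °F is Grade 2 in one unit and Grade 1 in the other

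*Protocol*

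**What the plan says.** Protocol 18.6, Miscellaneous, labels the row "Fever oral >12 hours". Its cells are:

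- Grade 1: "37.7 - 38.9C (100.0 - 101.5F" (bracket closes there).
- Grade 2: "39.0 - 39.5C (101.6 - 102.9F) OR max temp of 103F".
- Grade 3: "39.6 - 40.5C (103 - 105F) OR max temp of 103.5F".
- Grade 4: above 40.5 °C, with 105 °F in brackets, or a maximum above 105 °F.

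The maximum-temperature clauses are in Fahrenheit only. How they relate to the duration in the row label is not stated.

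The scale is put to use in section 6.9.2.1, which takes its fever definition from it ("rash and fever (as described in Toxicity Grading Scale, p. 58") and adds: "Frequencies and percentages of subjects experiencing each reaction will be presented for each symptom severity". Section 6.6.2.1 also points to the scale for fever seen at the 60-minute observation. Section 6.6.2.3 has the investigator grade events on the adverse event form "based on the Toxicity Grading Scale (Appendix 17.6) or if the event is not listed the event will be graded following these guidelines".

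The one fever threshold in the body text, for noting fever on the diary card (6.6.2.1), is above 38 °C. The text gives no unit for the oral temperatures that subjects record.

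**The concern.** A grading table that gives two units must give the same grade in both. Here the bracketed Fahrenheit figures read as conversions of the Celsius figures but are not, so the grade of some fevers depends on the unit in which the thermometer was read or the table consulted. The maximum-temperature clauses add a second ambiguity: 103 °F is both the Grade 2 maximum and the floor of the Grade 3 Fahrenheit band.

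Fever is a solicited systemic reaction, and 6.9.1 counts observed immunization reactions among the primary safety measurements of a small safety study. The split between mild and moderate fever is what the 6.9.2.1 table is meant to show. The investigator assigns grades from this table during the trial, so an analysis rule written later would come after any decision taken on them.

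**Working it through.** **Inputs.** The four printed bands in 18.6. Formulas: F = C × 9/5 + 32 and C = (F − 32) × 5/9.

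**Step 1: do the printed limits convert?**

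| Limit | Celsius printed | Converts to | Fahrenheit printed |
|---|---|---|---|
| Grade 1 floor | 37.7 | 99.86 | 100.0 |
| Grade 1 top | 38.9 | 102.02 | 101.5 |
| Grade 2 floor | 39.0 | 102.20 | 101.6 |
| Grade 2 top | 39.5 | 103.10 | 102.9 |
| Grade 3 floor | 39.6 | 103.28 | 103 |
| Grade 3 top | 40.5 | 104.90 | 105 |

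The outer limits agree to about 0.1 °F, which is ordinary rounding. The Grade 1/2 boundary is off by 0.5–0.6 °F (102.02 − 101.5 = 0.52; 102.20 − 101.6 = 0.60) and the Grade 2/3 boundary by 0.2–0.3 °F (103.10 − 102.9 = 0.20; 103.28 − 103 = 0.28). Rounding does not explain those.

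**Step 2: which readings change grade?** Each 0.1 °F reading is graded by the printed Fahrenheit band and, after conversion and rounding to 0.1 °C, by the printed Celsius band.

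- 101.6 °F = 38.67 °C and 102.1 °F = 38.94 °C, which round to 38.7 and 38.9 °C. All six readings from 101.6 to 102.1 °F are Grade 2 by Fahrenheit and Grade 1 by Celsius. The first reading on which both say Grade 2 is 102.2 °F = 39.0 °C.
- 103.0 °F = 39.44 °C and 103.1 °F = 39.50 °C: Grade 3 by the Fahrenheit band, Grade 2 by the Celsius band.
- At the edges, 99.8–99.9 °F (37.67–37.72 °C) is ungraded by Fahrenheit and Grade 1 by Celsius after rounding. These readings lie below the diary threshold of 38 °C (100.4 °F). Also, 105.0 °F (40.56 °C) is in the Grade 3 Fahrenheit band and above the Grade 3 Celsius band.

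The Fahrenheit Grade 2 band holds 14 readings (101.6 to 102.9 in tenths), so 6 of 14 are in conflict.

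**Step 3: the maximum-temperature clauses.** If they mean the peak, and the bands mean fever sustained beyond 12 hours, a brief 103.0 °F peak is Grade 2 and there is no conflict for it. If the bands apply to any reading, 103.0 °F is Grade 3 in Fahrenheit and Grade 2 in Celsius. The row does not say which reading is meant.

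**Step 4: do corrected limits close the gaps?** With Celsius governing and rounding to 0.1 °C, the first and last Fahrenheit readings of each grade are:

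- 99.8 °F (37.7 °C) to 102.1 °F (38.9 °C);
- 102.2 °F (39.0 °C) to 103.1 °F (39.5 °C);
- 103.2 °F (39.56, rounds to 39.6 °C) to 104.9 °F (40.5 °C);
- 105.0 °F (40.56, rounds to 40.6 °C) upward.

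These bands are contiguous and agree in both units. This check covers the bands alone; the peak clauses need the separate rule given in the fix.

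**The case against.** The strongest reply is that this is a conversion slip in one appendix row. Celsius is printed first, the only body-text threshold is in Celsius, and the diary card and case report form, which are not shown, may fix a unit. There is one clinical site and all arms enrol concurrently (6.5.3), so if one unit is used throughout, all groups are graded alike. The table is descriptive, and no test or power figure rests on it. Much of this stands. It limits the consequence but does not make the row right: Celsius is not declared to govern, and because the maximum-temperature clauses exist only in Fahrenheit, the row cannot be applied in Celsius alone.

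A reader might infer three stronger things that the protocol does not support.

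- **That the conflict changes who is called back to clinic.** After each immunization, section 6.5.6 says that if effects are deemed moderate, "he/she will be asked to return to clinic for evaluation by the investigator". The scale heads Grade 2 as moderate, but 6.5.6 refers to a reactogenicity worksheet, not to this scale. The effect follows only if the two uses of the word mean the same thing.
- **That the stopping rule in 6.6.2.2 misfires.** That needs a reading of 103.0–103.1 °F, the band rather than the peak clause (whose Grade 3 level is 103.5 °F), and a probable or definite relation to vaccination.
- **That the share of conflicting thermometer readings measures the share of subjects affected.** It does not. The protocol gives no expected distribution of temperatures.

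Section 6.6.2.3 is also weaker support than it looks. It sends reactions within 7 days to a separate reactogenicity form, so the link from solicited fever to this scale rests on 6.6.2.1 and 6.9.2.1.

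**Conclusion.** The point holds. The fever row is wrong as printed: the two units disagree by about half a degree Fahrenheit at the Grade 1/2 boundary, so 101.6–102.1 °F has two grades. A smaller disagreement at 103.0–103.1 °F is compounded by the double use of 103 °F. The Celsius grades at issue assume rounding to 0.1 °C; without rounding, 102.1 °F (38.94 °C) falls between the printed bands but is still below the Grade 2 floor.

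The established effect is on the mild and moderate counts in the 6.9.2.1 fever table. For scale, one subject moved between grades shifts a percentage by 1/12 = 8.3 points in a group of 12, or 1/8 = 12.5 points among the 8 active recipients. That is true of any event in groups this small, and it does not say how many subjects would move. Effects on clinic return and on stopping remain possible but conditional. This should be corrected because it is a wrong threshold that the trial uses and correcting it costs almost nothing; it does not put the study's conclusions in doubt.

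**What to change.** In 18.6, state that Celsius governs and that Fahrenheit readings are converted and rounded to 0.1 °C. Reprint the bands as:

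- Grade 1: 37.7–38.9 °C (99.8–102.1 °F)
- Grade 2: 39.0–39.5 °C (102.2–103.1 °F)
- Grade 3: 39.6–40.5 °C (103.2–104.9 °F)
- Grade 4: above 40.5 °C (105.0 °F or higher)

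State that these bands apply to fever sustained beyond 12 hours. Keep the maximum-temperature clauses as peak criteria and give them in Celsius: 103 °F = 39.4 °C (Grade 2), 103.5 °F = 39.7 °C (Grade 3), 105 °F = 40.6 °C (Grade 4). Read as a peak at or above the stated value, each rounded figure admits one tenth of a degree Fahrenheit more than the print: 102.9 °F (39.39), 103.4 °F (39.67) and 105.0 °F (40.56). Where the peak and the sustained criterion give different grades, assign the higher.

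Do not simply delete the peak clauses while the 12-hour label stays, because a short high fever would then have no grade. A brief fever that stays below the Grade 2 peak has no grade on this reading, as in the printed row, so add a sentence on how to tabulate it.

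The cost is the wording of one table row and any matching key on the diary card and case report form. No procedures, visits or subjects are added.
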